8.1 Efficacy Assessments

To evaluate the efficacy of ETC-1002, blood samples will be collected for the following fasting lipid assessments of 1) to 5) and assessments of 6) to 8).

The investigator or subinvestigator will instruct subjects to visit the trial site according to the schedule specified in [Table 1.3-1](#) under fasting conditions and collect blood samples. The investigator or subinvestigator will record the date and time of blood sampling and the fasting state at the time of blood sampling in the source document and the eCRF. The test results will be directly reported to the sponsor by the central laboratory selected by

the sponsor in electronic files. Therefore, it is not necessary to record the results in the source document and eCRF. The fasting state is defined as a state in which a subject has fasted (including abstaining from sugar-containing beverages such as juice) for 10 hours or more from the night before. If a subject cannot visit the trial site in a fasting state, the subject should visit the trial site again in a fasting state for blood sampling within the visit window for the same evaluation time point. If the subject cannot visit in the fasting state within the visit window for the same evaluation time point, this case will be recorded as a protocol deviation and the blood sample will be submitted as a sample in a fed state to the central laboratory. Each subject will visit the trial site without taking the IMP on the visit day.

Samples will be sent to the central laboratory, the results of which will be used for analysis. LDL-C values will be calculated using the Friedewald formula ($TC - HDL-C - TG/5$) and measured using the LDL-C direct method. Proper sample collection, handling, and shipping procedures will be provided to the trial sites in a separate manual prior to the start of the trial.

To maintain the blind of the trial, the results of the assessments 1) to 7) will not be reported to the trial site and the sponsor from the start of IMP administration on Day 1 (Visit T1) to Week 12 (Visit T6) (or to the completion of the withdrawal examination, if applicable). The test results will be stored strictly by the central laboratory, submitted to the trial site after unblinding, and provided to the sponsor in electronic files. In addition, measurement at the laboratory of trial sites is not allowed from the start of IMP administration on Day 1 (Visit T1) to Week 12 (Visit T6) (or to the completion of the withdrawal examination, if applicable).

- 1) LDL-C
- 2) HDL-C
- 3) non-HDL-C
- 4) TC
- 5) TG
- 6) apo B
- 7) hsCRP
- 8) HbA1c

8.2 Pharmacokinetic Assessments

The investigator or subinvestigator will instruct subjects to visit the trial site according to the schedule specified in [Table 1.3-1](#) without taking the IMP and blood sampling will be performed before IMP administration. On Day 1 (Visit T1) and Week 4 (Visit T3),

subjects will take the IMP at the trial site and blood sampling will be performed 2 to 4 hours after IMP administration in addition to pre-dose blood sampling.

8.2.1 Pharmacokinetic Plasma Samples

[figure not shown]
Blood samples (3 mL) will be collected in vacutainers containing ethylenediaminetetraacetic acid (EDTA) and processed into plasma to determine the concentrations of ETC-1002 and its active metabolite ESP15228. Additional metabolites that are not identified in the protocol may also be analyzed, if needed. In addition, PK samples may be used for the investigation of analytical methods, if needed.

The actual date and time of the PK sample collection and the date and time of IMP administration immediately before the sample collection will be recorded in the eCRF. The results of measurement will be reported directly from the bioanalytical laboratory to the sponsor, and therefore, recording in the eCRF is not required.

After processing into plasma, aliquots will be placed into appropriately labeled tubes and will be placed in a freezer set at -70°C or -20°C , unless otherwise instructed in the Operations.

All plasma samples will be shipped to the bioanalytical laboratory. Additional information will be provided in the manuals.

The bioanalytical laboratory will measure drug concentrations only in the samples of the ETC-1002 group after keeping a record of the use of the allocation table. The contents of the allocation table will not be disclosed to any persons other than those who are considered necessary for the duties by the bioanalytical study director and strictly store it. The bioanalytical laboratory will retain the results strictly and submit the electronic file to the sponsor after unblinding.

8.3 Pharmacodynamic Assessments

[figure not shown]
Pharmacodynamic assessments other than those described for efficacy assessments are not planned.

8.4 Pharmacogenomic Assessments

Not applicable.

8.5 Biomarker Assessments

Biomarker assessments other than those described for efficacy and pharmacodynamic assessments are not planned.

[REDACTED]

A horizontal bar chart illustrating the percentage of respondents who have heard of various terms. The y-axis lists 15 terms, and the x-axis shows percentages from 0% to 100% in increments of 10%. The bars are black.

Term	Percentage
1	98
2	95
3	92
4	90
5	88
6	85
7	82
8	80
9	78
10	75
11	72
12	70
13	68
14	65
15	62

Term	Percentage
GDP	98
Inflation	98
Interest rates	98
Central bank	98
Monetary policy	98
Quantitative easing	98
Inflation targeting	98
Interest rate hike	75
Interest rate cut	65
Inflationary spiral	98

A series of horizontal black bars of varying lengths, likely representing data points or categories in a bar chart. The bars are arranged in a grid-like pattern, with some bars being significantly longer than others, indicating a wide range of values or frequencies.

Three horizontal black bars of varying lengths are positioned side-by-side. The top bar is the shortest, the middle bar is the longest, and the bottom bar is the second longest. They are set against a white background.

[REDACTED]

Term	Percentage
Climate change	95
Global warming	100
Green energy	98
Carbon footprint	98
Sustainable development	95
Renewable energy	92
Emissions reduction	90
Green economy	88
Carbon tax	85

8.7 Safety Assessments

If a “new abnormality” or “exacerbation” is observed in the following observation/examination items after the start of the IMP administration which are judged to be clinically significant by the investigator or subinvestigator as compared to before administration, appropriate measures will be taken as necessary.

Details pertaining to the definitions, collection, reporting, and follow-up of AEs are described in [Section 8.8](#).

8.7.1 Clinical Laboratory Assessments

Clinical laboratory samples will be collected at the time points described in the Schedules of Assessments ([Table 1.3-1](#)) to perform the clinical laboratory assessments described in [Section 10.2](#). The total volume of blood to be collected during the trial will be documented in the ICF.

On the day of the tests shown in the Schedules of Assessments ([Table 1.3-1](#)), subjects will be asked to visit the trial site in a fasting state (at least 10 hours of fasting [including abstaining from sugar-containing beverages such as juice]) without taking the IMP, and blood and urine samples will be collected from each subject. If a subject cannot visit the trial site in a fasting state, the subject should visit the trial site again in a fasting state for blood sampling within the visit window for the same evaluation time point. If the subject cannot visit in the fasting state within the visit window for the same evaluation time point, this case will be recorded as a protocol deviation and the blood sample will be submitted as a sample in a fed state to the central laboratory. The date and time of blood sampling, date of urine sampling, and the fasting state at the time of blood sampling will be recorded in the source document and the eCRF. The sponsor will select a central laboratory for this trial. The test results measured by the central laboratory will be used to confirm the eligibility. Proper sample collection, handling, and shipping procedures will be provided to the trial sites in a separate manual prior to the start of the trial. The central laboratory will report the test results to the investigator or subinvestigator who confirms the results. The laboratory report will be officially documented by entering the date of confirmation and signing the report by the investigator or subinvestigator. The test results will be directly reported to the sponsor by the central laboratory in electronic files. Therefore, it is not necessary to record the results in the source document and the eCRF.

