10.2 Appendix 2: Clinical Laboratory Tests

The tests detailed in [Table 10.2-1](#) will be performed.

Table 10.2-1 Clinical Laboratory Assessments	
Hematology:	Serum Chemistry:
Red blood cell count	Alkaline phosphatase
Hemoglobin	ALT
Hematocrit	AST
Mean corpuscular hemoglobin concentration	Total bilirubin
Mean corpuscular volume	Gamma glutamyl transferase
White blood cell (WBC) count	Total protein
WBC count with differential (neutrophils, eosinophils, basophils, monocytes, and lymphocytes)	Albumin
Platelets	Lactate dehydrogenase
Urinalysis (parameters other than pH and specific gravity will be included in the qualitative urinalysis)	
pH	Blood urea nitrogen
Protein	Creatinine
Glucose	Uric acid
Occult blood	CK
Bilirubin	Serum electrolytes (sodium, potassium, chloride, calcium, bicarbonate)
Urobilinogen	Glucose
Specific gravity	
Ketones	

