3.4 Trial Visit Window

Data observed at CRF Visit will be used at each analysis visit (but data at discontinuation will not be used in analysis). Data from unscheduled visits will not be used. Efficacy analysis will be performed using the data obtained up until 2 days after final IMP administration. In assessment of efficacy endpoints, baseline for fasting lipid parameters is defined as the mean of the values for Day 1 (Visit T1) and Week -1 (Visit S3). If only one value is obtained, that value will be used as baseline. For efficacy endpoints other than fasting lipid parameters, baseline is defined as the value for Day 1 (Visit T1). For safety endpoints, baseline is defined as the last data obtained prior to initial IMP administration in the treatment period.

4 Sample Size

Differences in the percent change in LDL-C from baseline to Week 12 in the ETC-1002 group versus the placebo group in non-Japanese phase 3 trials were -18.1% and -17.42% in trials in statin tolerant subjects and -21.41% and -28.45% in trials in statin intolerant subjects. Based on the results, the difference between the ETC-1002 group and the placebo group in the subjects with statin tolerance was assumed to be 17% , and the difference between the ETC-1002 group and the placebo group in the subjects with statin intolerance was assumed to be 25% . For the present trial it was assumed that the percentage of statin intolerant subjects enrolled would be 20% and that the difference in the endpoint between the ETC-1002 group and the placebo group would be 19% in the overall trial population. Based on the results of the phase 3 trials, assuming a difference of 19% with standard deviation of 25% between the ETC-1002 groups and the placebo group in the percent change in LDL-C from baseline to Week 12, 38 subjects per group are required to achieve a power of 90% or higher in a two-tailed test with a 5% significance level. Assuming a withdrawal rate of 12.5% , the target number of subjects to be randomized was set at 44 per group.

5 Statistical Analysis Datasets

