5.4 Handling of Missing Data

In the primary analysis of the primary endpoint, when the LDL-C value at Week 12 is missing, the missing value will be imputed using the last value observed from after initial IMP administration up until 2 days after final IMP administration (last observation carried forward: LOCF).

In analysis of the percent change from baseline to Week 12 for secondary endpoints and of the proportion of subjects achieving the lipid management goals of LDL-C, missing values will be handled in the same manner as above. Missing values will not be imputed for sensitivity analysis and pharmacokinetic analysis.

Fasting lipid parameters will be handled as shown in the table below.

Condition	Fasting Lipid Parameters
Parameter to be used in analysis, irrespective of fasting condition	LDL-C (direct measurement)
Parameters to be used in analysis only when obtained under a fasting condition	LDL-C (Friedewald formula), HDL-C, non-HDL-C, TC, TG

6 Primary and Secondary Outcome Variables

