9.3 Clinical Laboratory Data

Among parameters of the urinalysis in the laboratory tests, the qualitative urinalysis includes parameters other than pH and specific gravity.

For parameters other than qualitative urinalysis, descriptive statistics of the actual value and change from baseline will be calculated at each visit. For qualitative urinalysis parameters, shift tables at each visit from baseline will be prepared. For parameters other than qualitative urinalysis, measured values will be categorized using the reference range to “below the lower limit of reference range”, “within the reference range” and “above the upper limit of reference range”, and shift tables at each visit from baseline will be prepared.

The number and percentage of subjects meeting the criteria for identifying laboratory values of potential clinical relevance ([Appendix 2: Criteria for Identifying Laboratory Values of Potential Clinical Relevance](#)) will be calculated.

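### SAP 9.3 pools fed and fasting serum glucose in its summaries and shift tables, although Appendix 2 separates them and the eCRF records fasting state

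*Protocol*

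**What the plan says.** Protocol 8.7.1 asks subjects to attend after at least 10 hours of fasting. A subject who does not is to come back fasting within the same visit window. If that also fails, the case becomes a recorded protocol deviation and "the blood sample will be submitted as a sample in a fed state to the central laboratory". The section also states that "the fasting state at the time of blood sampling will be recorded in the source document and the eCRF". On reporting it makes no exception for fed samples: "The test results will be directly reported to the sponsor by the central laboratory in electronic files". Table 10.2-1 includes glucose under serum chemistry.

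The SAP takes fasting state into account in two places:

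- **SAP 5.4** introduces its rule with "Fasting lipid parameters will be handled as shown in the table below". The row labelled "Parameters to be used in analysis only when obtained under a fasting condition" holds Friedewald LDL-C, HDL-C, non-HDL-C, TC and TG. Directly measured LDL-C is used whatever the fasting state. Glucose is not in the table.
- **SAP Appendix 2** gives glucose two criteria for potential clinical relevance: 126 mg/dL or more if fasting, and 200 mg/dL or more if not.

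SAP 9.3 does not: "For parameters other than qualitative urinalysis, descriptive statistics of the actual value and change from baseline will be calculated at each visit". The same values are then sorted into low, normal and high against the reference range for the shift tables. SAP 9 adds a Week 12 (LOCF) version of the safety analyses. The general rule in SAP 3.4 is "Data observed at CRF Visit will be used at each analysis visit". It leaves out discontinuation and unscheduled data but says nothing about fasting state. Protocol 9.4.2.2 has no fasting condition either, and SAP 14 lists no change on this point.

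**The concern.** Glucose rises after a meal. If a fed value after dosing is compared with a fasting baseline, the difference includes a meal effect but appears as a change on treatment, and may appear as a move into the high category. The reverse pairing hides a rise. Exclusion criterion 7 bars type 2 diabetes only when it is uncontrolled with HbA1c of 9% or more, so some enrolled subjects may have large post-meal values.

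The SAP is also not consistent with itself here. Appendix 2 makes fasting state decide whether a given glucose value counts, while SAP 9.3 ignores it, although the variable is collected. What is at stake is how readable one descriptive safety parameter is in a trial with 44 randomized subjects per arm, where a few values can move a group mean.

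**Working it through.** The plan states no figure on this point, so there is none to reproduce. The check has two parts.

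**1. Following one fed sample through the plan.** Suppose a subject has a fed serum glucose of 180 mg/dL at a scheduled visit.

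- Protocol 8.7.1: the sample is sent, the result reaches the sponsor, and the eCRF marks it as fed.
- SAP 3.4: the value belongs to a scheduled visit, so it is used.
- SAP 5.4: the fasting restriction covers lipids, so the value is not removed.
- Appendix 2: it is non-fasting and below 200 mg/dL, so it is not counted as potentially clinically relevant. A fasting 180 mg/dL would be counted.
- SAP 9.3: it enters the mean and the change from baseline. It is classed as high in the shift table if it exceeds the laboratory's upper limit. The documents do not show that limit; I assume it lies below 180 mg/dL.
- SAP 9: if later values are missing, it can be carried forward to Week 12.

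Applied exactly as written, the SAP therefore pools fed and fasting glucose in every SAP 9.3 output except the Appendix 2 counts.

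**2. Illustration of size.** All inputs except the 44 per arm are assumptions.

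- Fed proportion f = 0.05 (range 0.02 to 0.10).
- Fed-minus-fasting difference d = 60 mg/dL (range 30 to 60).
- SD of the fasting change s = 15 to 20 mg/dL.
- n = 44, the randomization target per arm (Protocol 9.1).

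*Mean at a visit.* Shift = f × d = 0.05 × 60 = 3.0 mg/dL. Over the range it runs from 0.02 × 30 = 0.6 to 0.10 × 60 = 6.0 mg/dL.

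*Mean change from baseline.* Shift = (f after dosing − f at baseline) × d. If every baseline is fasting, this is again 3.0 mg/dL. If the fed rate is the same at baseline, it is (0.05 − 0.05) × 60 = 0.

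*Spread of the change.* With fasting baselines, SD = √(s² + f(1 − f)d²), where f(1 − f)d² = 0.0475 × 3600 = 171.

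- s = 20: √(400 + 171) = 23.9, an increase of 19.5%.
- s = 15: √(225 + 171) = 19.9, an increase of 32.7%.

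If baseline is fed at the same rate, independently, the extra term doubles to 342.

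- s = 20: √742 = 27.2, an increase of 36%.
- s = 15: √567 = 23.8, an increase of 59%.

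Equal fed rates thus remove the expected shift but add noise.

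*Difference between arms.* With equal fed rates the expected difference is zero. The number of fed samples per arm averages 0.05 × 44 = 2.2. Two arms differ by 2 or more with probability 0.45 (0.23 at 2% fed, 0.59 at 10%). An imbalance of 2 moves the difference in means by 2/44 × 60 = 2.7 mg/dL. For comparison, the standard error of that difference with s = 20 and no fed samples is 20 × √(2/44) = 4.3 mg/dL.

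**The case against.** Four arguments on the other side carry weight.

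- *The threshold counts are protected.* A reader might infer that the SAP has a fasting rule for lipids alone. Appendix 2 contradicts that: its glucose criteria are split by fasting state. Only the inclusion rule in SAP 5.4 is confined to lipids. A reader might also infer that the SAP treats fed glucose as if it were fasting. It never says so; it simply does not separate the two. This stands, and it limits the point to the SAP 9.3 summaries and shift tables.
- *Fed samples should be rare and balanced.* They arise only after a failed fasting revisit, as a recorded deviation, and blinded randomized arms give no reason to expect different rates. This stands. It rules out reading the point as a bias between dose groups, but not the noise or the chance imbalance.
- *Little depends on serum glucose.* It is descriptive and untested. HbA1c, which Protocol 8.1 lists apart from the fasting lipids, is a secondary endpoint with its own analysis of covariance. Laboratory values and deviations are also listed by subject. This stands, and it keeps the point minor.
- *Summarizing all observed safety data is a defensible choice.* It is, and with a fasting-only rule a fed Week 12 value would give way to an earlier fasting one in the LOCF summary. But the sponsor has already decided, for most lipids and for the Appendix 2 glucose criteria, that fasting state changes what a value means. Flagged listings keep the fed values in view.

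**Conclusion.** The point holds as a small, avoidable weakness. SAP 9.3, followed as written, mixes fed and fasting serum glucose in the means, changes from baseline, Week 12 (LOCF) summary and shift tables, while the SAP's own Appendix 2 keeps them apart. The consequence is extra variability, chance imbalance between arms and probably some spurious entries in the high category.

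The size is unknown. The documents give no fed rate, no fed-minus-fasting difference, no SD for glucose and no glucose reference range. The illustrated 3 mg/dL shift and the increases in SD rest wholly on assumed inputs, and for changes from baseline the shift disappears if baselines are fed equally often. A reader might infer a distorted treatment comparison. The documents do not support that, because the expected difference between arms is zero when fed rates are equal.

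The primary endpoint is unaffected: SAP 8 uses directly measured LDL-C, which SAP 5.4 accepts irrespective of fasting. This is a cheap improvement, not a defect that threatens the trial's conclusions.

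**What to change.** Add one sentence to SAP 9.3: descriptive statistics, changes from baseline, the Week 12 (LOCF) summary and reference-range shift tables for serum glucose use fasting samples only, at baseline and after baseline. State in the same place that fed values stay in the laboratory listing with a flag and remain countable under the Appendix 2 non-fasting criterion. The sentence belongs in SAP 9.3, since the SAP 5.4 table is specific to lipids. Record the restriction in SAP 14 as a change from Protocol 9.4.2.2.

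The cost is one sentence and one filter on a variable already in the eCRF. A few observed values drop out of the glucose summaries, a subject whose only baseline glucose is fed has no change from baseline, and an occasional fed Week 12 value is replaced in the LOCF summary by an earlier fasting one. Reporting the number of fed samples excluded per arm and visit would show how much was lost.

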8.7.2 Physical Examination

Physical examinations will be performed at the time points described in the Schedules of Assessments (Table 1.3-1). The investigator or subinvestigator will perform physical examinations for the following test items by methods such as interview and record the results in the source document. For consistency of assessments, it is recommended that all physical examinations for individual subjects be performed by the same physician throughout the trial. At Week -5 (Visit S1) and Day 1 (Visit T1), the dates and results of the examinations will be recorded in the source document and the eCRF. At other time points, only the date of the examination will be recorded. If clinically significant physical findings, which are compared with Week -5 (Visit S1) during the screening [REDACTED] [REDACTED] and compared with Day 1 (Visit T1) during the treatment and follow-up periods, are observed, those findings will be recorded as AEs.

Test items: HEENT (head, eyes, ears, nose, throat), chest, abdomen, genitourinary, extremities, nerves, skin/mucosae

8.7.3 Vital Signs

Vital signs will be collected at the time points described in the Schedules of Assessments ([Table 1.3-1](#)) after resting for at least 5 minutes and before blood sampling. Subjects should be monitored for potentially clinically significant vital signs values. Body temperature, systolic and diastolic blood pressure, and pulse rate will be measured in the sitting position after resting for at least 5 minutes according to the procedures specified by the trial site. The date, time, and results of body temperature, systolic and diastolic blood pressure, and pulse rate measurements will be recorded in the source document and the eCRF.

